## **PURPOSE OF STUDY AND BACKGROUND**

### **Objective**

Dementia is a common problem for older patients presenting to emergency departments (EDs) and for their family caregivers who often lack the support, understanding, and skills to manage the myriad of problems that may be related to the need for that ED visit. The purpose of the Program of Intensive Support in Emergency Departments for Care Partners of Cognitively Impaired Patients (POISED-CPCIP, hereon referred to as POISED) randomized controlled trial is to use previously established quality improvement methods of root cause analysis to uncover reasons for ED use and to focus on caregiver (CG) activation within a program of dementia care management. Study goals are to reduce recurrent ED visits and improve caregiver symptoms of depression, anxiety and need for social support. POISED, a 4-year study, will test whether a novel care management intervention for family CGs of ED users with cognitive impairment and likely Alzheimer's disease and related dementias will reduce ED use at 3 and 6 months over the intervention period. In addition to ED use, we will test whether CGs exposed to the intervention will experience greater improvements (compared to controls) in family caregiving confidence in managing the healthcare needs of the care recipient (CR), and improved anxiety, depression and sense of social support.

### **Background**

The United States spends more than \$100 billion providing care for the millions of individuals and their family caregivers (CGs) affected by Alzheimer's disease and related dementias (ADRD). By 2050, 11–19 million people in the U.S. will have ADRD with the associated projected annual Medicare costs exceeding one trillion dollars. Most patients with ADRD have suboptimal management of their cognitive, behavioral and functional disability and this is made worse by under-recognition. The unmet needs of family CGs challenge chronic disease management and necessitate high levels of acute care. Compared with those without dementia, patients with ADRD visit the emergency department (ED) more often, are more likely to return within 30 days, and are more likely to die after an ED visit. Despite such concerns, the role of ADRD as a factor in ED use is likely unrecognized, not typically addressed, and may be much larger than anticipated.

An ED visit represents a “sentinel event”—either a failure in managing a chronic condition or the occurrence of new symptoms or problems—and is typically prompted by the need for urgent attention. Although the presenting symptom provides a sharp focus for ED care and is usually addressed before the patient is sent home, EDs do not deploy strategies to uncover or address symptom precipitants or root causes—those key contextual factors that contribute to ED use. Among those contextual factors are the presence of unrecognized dementia or cognitive impairment in the patient and the caregiving situation at home. In general ED care does not address the needs of CGs (used here to mean key family and friends of persons with ADRD) in managing the presenting problem and the ED discharge plan at home. Concerns about the needs of CGs of persons with ADRD have motivated the development of dementia care management programs. However, such programs do not focus specifically on high-risk or high-need patients, do not use the need for ED care of patients with comorbid chronic disease as an organizing principle to engage and empower CGs in their healthcare management, and do not view CGs as care partners. Moreover, care management programs are not typically

offered at the crisis-point of an ED visit. Whereas some EDs now use cognitive assessment as part of their routine evaluation, the efficacy of dementia care management initiated at the point of an ED visit has not been tested.

This proposal benefits from the recent decisions of two large academic institutions to include cognitive screening as part of ED care for older patients.

*Of note, cognitive screening is not part of the experimental design; thus, patients are not being consented to undergo cognitive screening.*

We propose to conduct a randomized controlled trial of care management, POISED, for caregivers of patients who fail a cognitive screening test at the point of an ED visit and are discharged to home. We will randomize dyads—family caregivers and their care-recipient (CR) patients—to POISED or to a usual care control group. Within POISED, we will identify root causes of ED visits (using root cause analysis, RCA) and apply this to focused care management protocols and interventions.

### **Specific Aims**

The specific aims of this proposal are to:

- 1) **Test whether the POISED intervention will reduce recurrent acute care use over 6 months when compared with post-ED care for dyads without POISED. We hypothesize that recurrent acute care use over 6 months will be less for CRs whose family CGs participate in POISED.**
- 2) **Test whether the 6-month POISED intervention will improve family caregiver “activation” in managing the health care of care recipients compared with post-ED care without POISED at 3 and 6 months. We hypothesize that POISED will improve family CG activation in managing the health care of CRs.**
- 3) **Test whether POISED will improve caregiver psychosocial outcomes compared with post-ED care without POISED at 3 and 6 months. We hypothesize that CG depression, anxiety, and experience of social support will improve more for CGs who are enrolled in POISED than for those referred to other care management programs.**

**Potential Impact:** Studying this approach may lead to low cost strategies to reduce high cost acute care use and related improvements in CG ability to assist in chronic disease management for CRs with dementia. Related impacts are improved health of CRs and psychosocial well-being of CGs.

### **METHODS**

**Setting:** The study will be conducted in two cities, New York and Indianapolis, in the EDs of their respective academic institutions—NYU Langone Medical Center and Indiana University Health University Hospital. The NYU Ronald O. Perleman Center for Emergency Services sees >60,000 patients annually. In 2015 the numbers of ED patients >75 years who were discharged to home were >3700 in the NYU ED and 2400 patients in the Indiana University Eskanazi and Methodist EDs.

**Aim1: Recruit and randomize a sample of 900 patient-caregivers (CGs) dyads (1800people total) presenting to the ED and test whether the POISED intervention will reduce recurrent acute care use over 6 months when compared with post-ED care for patients and CGs without POISED.**

**Study Design:** We will randomize subjects to either usual care or interventional groups where we will perform an initial assessment and provide a novel care management intervention for family CGs of ED users with cognitive impairment and likely ADRD.

***Inclusion/Exclusion Criteria for Care Recipients:***

Inclusion criteria for participation in care management or usual care are as follows:

- 1) Must be 75 years and older
- 2) Must be in the emergency department for care at the point of recruitment
- 3) Must be English- or Spanish-speaking
- 4) Must have a family member or friend who provides caregiving assistance
- 5) Must have a plan to be discharged to home
- 6) Must have scored < 4 on the MiniCogTM15-19 or if using caregiver assessment by IQCODE, must be > 3.4
- 7) Must have capacity to consent or have a proxy.

Exclusion criteria for participation in care management or usual care are as follows:

- 1) Care recipient (CR) is a resident of a nursing home or other supportive facility
- 2) CR scores  $\geq 3$  on the MiniCogTM or the caregiver assessment by IQCODE was  $< 3.4$
- 3) Caregiver (CG) declines participation
- 4) CR is not being discharged to home

CR does not allow their family member or emergency contact to be contacted

Note: If the care recipient lacks capacity and we cannot obtain consent from their proxy, we will not access those data or include them in any analyses. Please note that a caregiver can still participate in the study with the assent of the care recipient, without the use of the health care data.

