*Recruitment:* Potential subjects will be identified from the ED on the basis of the cognitive state of the ED patient. Family caregivers will be identified and approached in the ED and if not present, will be contacted by phone and offered participation in the study. Potential subjects (caregivers) are identified by the treating team who have no direct involvement in the research. As is typical for these kind of clinical studies, the treating team, using clear inclusion and exclusion criteria will ask potential subjects whether or not a research assistant (RA) (from the POISED team) can speak with them to tell them about an opportunity to participate in a study. The treating team is never informed as to whether a potential subject agrees to participate or refuses after meeting with the RA. Caregivers and/or care recipients who are in the ED will be approached only after we (the POISED team) are given permission from the ED staff who will alert the research assistant of a potential caregiver-care recipient dyad. Caregivers and their care recipients will be informed that declining to participate will in no way impact their care in the emergency department or elsewhere and that the treating medical staff will not know about their decision as to their agreement or refusal of participation.

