After ED staff have completed cognitive assessment using the Mini-Cog™ and given us permission for to speak to the dyad, we will approach and offer participation to CGs and ED patients > 75 years who have scored <=3/5 on the Mini-Cog™ and have plans to be discharged home. A score of >3.4 on the Short IQ-CODE (a proxy tool used by ED staff) will identify those few who cannot complete the Mini-Cog™. We will consent CGs and care-recipients at the time of ED visit. (See Recruitment, Consent, and Assent). If the care recipient lacks capacity, we will attempt to consent to identify and consent the Care Recipient via a proxy (See Recruitment, Consent and Assent) If there is no available or identified CG, we will attempt to identify and consent the CG at a later date either by phone (using an IRB approved verbal consent telephone script with waiver of written documentation of consent) or in person using an IRB approved consent form to obtain written consent. Please note that the study team will maintain a deidentified record (using a linking code) of who had been approached (in person or by phone), whether they had declined or accepted to participate in the research, and at what time and on what date this conversation took place.

*Phone Recruitment:* In the event that ED recruitment and assessment cannot be done in person, a Phone Recruitment Protocol will take effect. Potential subjects will be identified from the ED on the basis of a recent admission to a participating ED site location, using the EMR. Family caregivers will be identified by the patient, or via the EMR (i.e. Emergency Contact). In order to contact a family caregiver, the person who was the ED patient will need to be called by telephone first. If the patient gives any indication of not wanting research staff to call their family member or emergency contact, research staff will not attempt to call that person and the patient and care partner will no longer be eligible to participate. A recruiter will attempt to contact the patient within 48 hours of their discharge from the ED to assess willingness to participate and our interest in contacting the designated care partner. When a Mini-Cog cannot be administered in person, the study team member will contact a Care Partner (if no refusal by the patient to do this) and will conduct the IQCODE with that care partner. After assessment for eligibility, informed consent will be obtained over the phone.

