*Randomization:* A web-based randomization scheme will be used to randomize participants to intervention or usual care groups in blocks of four or six stratified by: site (NYU or IU), English or Spanish speaking, whether the care partner lives with the CR, and Mini-Cog™ score less than or equal to 3 (or IQCODE of >3.4).

. We assume a positive IQ-CODE score (>3.4) with an inability to complete a Mini- Cog™ is equivalent to a Mini-Cog™ score of 0.

*Initial assessment phase:* The POISED care management team consisting of specially-trained nurses functioning as care managers (CMs) and para-professionals in the role of care manager assistants (CMAs) will conduct a biopsychosocial/environmental needs assessment by phone within 48 hours of emergency room discharge if not possible during the ED stay. These team members are clinical professionals delivering a clinical service. They are not research staff or delivering experimental procedures. This assessment includes a demographic and psychosocial interview focused on achieving problem identification. The program uses standardized assessment tools including "Managing Your Loved One's Health" (MYLOH™) for chronic disease management and BEHAVE 5+ to identify problem behaviors common in advancing dementia that have been associated with caregiver strain, challenges to caregiving at home and in long-term care. BEHAVE 5+ also identifies proven behaviors common in prescribing of psychotropic medications to people with dementia. (See Appendix 3) If the consented CG is not available, we will attempt to complete the CG questions at a later date either by phone or in person.

*Root Cause Analysis:* Starting with the ED visit and working backwards in time, the team will explore and identify problems or branch-point situations that progressed to the need for ED care. Using a logic tree as a cause and effect approach to create a timeline of events leading to ED visit and asking the question, "how could this occur?" or "why" based on the "Five-Whys" strategy, the CM team will ask "why" for each successive answer, starting with "why did you come to the ED." Answers will be applied to medical record review looking for other possible triggers and opportunities for intervention. This brainstorming/investigative process to improve quality is also deployed by patient safety teams investigating adverse events.

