### **Recruitment, Consent and Assent**

Cognitive assessment is a usual care procedure for these emergency departments as part of the evaluation of patients 75 years and older who present to their emergency department. Eligible caregivers provide care for patients to be discharged home who perform poorly on the screening assessment defined by specific cut-points as abnormal (MiniCog™ < 3). If the patient is unable to be assessed but identified by the caregiver as having impairment consistent with likely dementia (IQCODE > 3.4) the caregiver will be considered eligible (see inclusion/exclusion criteria above, see page 3).

*The first stage of recruitment and consent is to determine the eligibility of the caregiver.* The caregivers of the eligible patients are considered for study recruitment and the caregivers will be approached in the ED or by phone (if Phone Recruitment in effect) and offered research participation. Only caregivers of those patients scheduled to be discharged home will be considered eligible for participation. If a caregiver is not present in the ED and a patient provides permission to contact that person, we will conduct consent procedures by telephone.

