*The second stage of recruitment and consent is consent of the Care Recipient for access to health records.* After it is determined that the Care Recipient has an eligible Caregiver, the Care Recipient will be approached regarding allowing the research team access to their medical records. Capacity is determined for the CR for consent using a common sense procedure. This is possible because the request in question is easy to understand procedure (collecting information from the health record). We anticipate that most will demonstrate capacity to decide regarding use of their medical records. For those who do not, we will use a proxy consent –the caregiver if that person is next of kin (defined based on hierarchy: spouse, child, sibling, nephew or niece) in the absence of a DPOA for healthcare or by consenting the proxy who is DPOA but not present, which again will require discussion of the consent process via telephone using an IRB approved script and mailing the original consent for to be signed or returned via mail, fax, or SendSafe email procedure for e-consent. If the care recipient does not want us to use his/her medical records we will of course not do so and for those subjects, and this will be missing data. This is a minimal risk study with a chart review being completed 6 months later; we will not require capacity to be reassessed at the end of the 6 months. We request consent at the beginning of the study because this is an element of the research protocol and both caregivers and care recipients need to be aware and agree with participating given this approach. Loss of capacity after giving permission does not negate this consent and require a new consent procedure but a caregiver (legal healthcare proxy) under these circumstances, can override the consent at any point in the study if in the future, the proxy does not want us to have access to the chart at the end of 6 months. The Care Recipient, as the consenting individual, can also always rescind their earlier consent. Please note that at the time of capacity assessment, the only clinical information that we have on this patient is that they have performed below a pre-specified cut point on a simple 2 minute cognitive screening test. This result neither indicates a definitive diagnosis of dementia, nor any level of severity of cognitive impairment.

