Sample Size and Power Consideration: Sample size for the proposed study is estimated for achieving 80% power in reducing acute care use in the POISED group compared with the usual care group in Specific Aim 1. A previous study had reported a 30-day readmission rate of 58% in dementia patients as compared to 38% in those without dementia. Given that our patient sample may include less severe cognitive impairment with less ED use, we assume, conservatively, that the rate of ED visits in the usual care group is 40%. With 320 patients enrolled per group, we will have 82% power to detect an odds ratio of 0.62 for repeat ED visits in the POISED group compared to the usual care group at the 0.05 significance level. This detectable odds ratio is equivalent to reducing the ED visit rate to 29% or lower in the POISED group compared with the 40% assumed for the control group. The use of stratified randomization ensures that patients in the intervention and control groups are similar on the stratification variables, thus reducing the variance of the difference between the two group means and resulting in greater power than simple randomization. Therefore, actual power for our study will be higher than projected here. Since we will be using EMR for acute care data and phone follow-up to supplement out of network use, we anticipate complete data from all study participants for this aim.

For Aims 2 and 3, assuming that 205 (64%) dyads will complete the 6-month evaluation (see Figure 2), we will have 80% power to detect an effect size of 0.28 or greater on the CG activation score, PHS-9, GAD-7 and MOS scores between POISED group and the control group using a two-sample t-test at the 0.05 significance level. The detectable effect size of 0.28 used in our power estimation is reasonable and justified given that previous studies on collaborative care management of dementia patients have shown an effect size of 0.45 SD on a number of caregiver psychosocial outcomes. Our previous studies have found a mean PHQ-9 score of 4.4 (SD=5.6), and a mean GAD-7 score of 3.2 (SD=3.5). Thus our projected effect size will allow us to detect a change as small as 1.6 on the PHQ-9 and 1 on the GAD-7. As described above, the use of stratified randomization will provide greater power than those projected here.

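### The Mini-Cog entry rule contradicts itself at a score of exactly 3, and the cognitive stratification factor as written covers every eligible care recipient

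*Combined protocol and SAP*

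**What the plan says.** Four places in the combined protocol and SAP state who enters on the Mini-Cog.

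- Inclusion/Exclusion Criteria for Care Recipients, inclusion item 6: "Must have scored < 4 on the MiniCog", with an IQCODE above 3.4 as the alternative.
- Same list, exclusion item 2: "CR scores $\geq 3$ on the MiniCog".
- Methods, Recruitment paragraph: participation is offered to dyads with patients "who have scored <=3/5 on the Mini-Cog™ and have plans to be discharged home".
- Recruitment, Consent and Assent: poor performance on the screen is "defined by specific cut-points as abnormal (MiniCog™ < 3", followed by a reference back to the inclusion and exclusion list.

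Two further places use a Mini-Cog value to define a stratification factor, not an entry rule. The Randomization paragraph names "Mini-Cog™ score less than or equal to 3 (or IQCODE of >3.4" as the fourth factor, after site, language and living arrangement. The Statistical Plan repeats a Mini-Cog of at most 3 as the cognitive variable to be controlled for. It then remarks that a cut at 0 or 1 tracks functional disability better than a cut at 3, and it groups IQCODE entrants with those scoring 0.

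**The concern.** Eligibility should give one answer for each patient. Here a patient scoring 3 meets an inclusion criterion and an exclusion criterion of the same list, is to be offered the study under the Recruitment paragraph, and is not abnormal under the consent section. Screening is delegated: "the treating team, using clear inclusion and exclusion criteria will ask potential subjects" whether a research assistant may approach them, and recruitment runs in emergency departments in two cities. Staff who work from different sections would treat the same patient differently. Enrolling the patient breaches exclusion item 2; not offering participation departs from the Recruitment paragraph. What is at stake is a consistent definition of the trial population and consistent screening.

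The stratum raises a related problem. The Aim 1 logistic model and the Aim 2 and 3 mixed models all adjust for the cognitive stratification variable. If everyone enrolled falls in a single level of it, that part of the stratification and of the adjustment is empty.

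**Working it through.** No figure in the plan is at issue, so the check is an enumeration. The Mini-Cog takes whole scores from 0 to 5 (the Recruitment paragraph writes the rule out of 5).

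**Entry rules**

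| Place | Rule | Scores admitted | Score of 3 |
|---|---|---|---|
| Inclusion item 6 | below 4 | 0, 1, 2, 3 | in |
| Exclusion item 2 | 3 or more excluded | 0, 1, 2 | out |
| Recruitment paragraph | 3 or less | 0, 1, 2, 3 | in |
| Recruitment, Consent and Assent | below 3 | 0, 1, 2 | out |

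1. Scores that are both included by item 6 and excluded by item 2: {0, 1, 2, 3} ∩ {3, 4, 5} = {3}.
2. Scores admitted by the Recruitment paragraph but not by the consent section: {0, 1, 2, 3} minus {0, 1, 2} = {3}.
3. All four rules agree on 0, 1, 2 (eligible) and on 4, 5 (not eligible). The disagreement is 1 of 6 values, and the statements split 2 to 2.
4. Search for a tie-break: the consent section points back to the criteria list, which contains the conflict. No other sentence ranks the statements.

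**Stratum**

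1. As written, the stratum is Mini-Cog in {0, 1, 2, 3}, or IQCODE above 3.4.
2. If entry is 0 to 3: eligible scores outside the stratum = {0, 1, 2, 3} minus {0, 1, 2, 3} = none (0 of 4).
3. If entry is 0 to 2: {0, 1, 2} minus {0, 1, 2, 3} = none (0 of 3).
4. IQCODE entrants must exceed 3.4 to be included, so all of them are inside it too.
5. The factor therefore has one occupied level. It creates no separate randomization lists. As a covariate it is a constant, which cannot be separated from the intercept, so it adjusts for nothing.

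**The case against.** The best defence of the entry rule is the usual convention that a patient must meet every inclusion criterion and no exclusion criterion. Read that way, the criteria list gives 0 to 2, which agrees with the consent section. This has force: it would be too strong to infer that the population is undefined, because one ordinary reading of the list gives a definite answer. It does not remove the conflict, since the documents never state the convention and the Recruitment paragraph says the opposite for a score of 3.

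A reader might lean the other way and count the two stratum statements as further votes for admitting 3. They are weak evidence, because they do not work as written and a stratification factor is not an entry rule. The consent section's remark that "they have performed below a pre-specified cut point on a simple 2 minute cognitive screening test" does not help either; it is descriptive and fits both thresholds.

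A reader might also infer a loss of power if milder patients come in. The documents do not support that. It would need the share of patients scoring 3 and their rate of ED visits, and neither is given. The sample size section bases its 40% control rate on an allowance for mildness ("Given that our patient sample may include less severe cognitive impairment with less ED use"), so milder cases may already be counted. The only figure it gives for people without dementia is 38% at 30 days, close to that 40%. The Methods also plan 900 dyads, against the 640 (2 × 320) in the power statement.

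On the stratum, the wording may be shorthand for a split that the randomization system does apply. That is possible, and the Statistical Plan's remarks on a cut at 0 or 1 point towards it, but no level boundary is given.

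**Conclusion.** The contradiction holds, at a score of exactly 3 and nowhere else on the scale. It is a conflict between operative statements with no stated precedence, and different sections would send the same patient different ways. Its size in dyads, and any effect on enrolment, event rate or power, is not computable from the documents. Nothing here suggests bias between arms. Care recipients who enter by IQCODE, including those recruited by phone, are unaffected.

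The linked defect also holds as written: the cognitive factor contains every eligible care recipient under either threshold. Whether the trial in practice stratified on cognition depends on how the web-based system coded the factor, which the documents do not show. The other three factors are untouched by this point.

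Both should be fixed. The conclusion rests on the text alone and needs no assumption beyond whole-number scores from 0 to 5.

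**What to change.** **Entry rule.** Reconcile inclusion item 6, exclusion item 2, the Recruitment paragraph, and Recruitment, Consent and Assent to one Mini-Cog threshold, and put that threshold on the screening form. Which threshold applies is for the sponsor to decide; this review does not choose.

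**Stratum.** In the Randomization paragraph and the Statistical Plan, restate the cognitive factor as a split within the eligible scores, with each level spelled out and the place of IQCODE entrants stated. The Statistical Plan appears to intend such a split. Before fixing the wording, check how the randomization system codes the factor, so that the analysis models use the factor that was actually applied. Confirm too that the score itself is kept, since the measures table in Appendix 1 lists no Mini-Cog variable.

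**Cost.** Wording changes in these places, the screening form, and one check of the randomization system. No new visits.
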